
sufficient evidence to support a large-scale clinical trial testing whether CPAP improves clinical outcomes in IPF. This will be achieved through three Specific Aims:

Specific Aim 1: Determine whether greater OSA severity is associated with higher levels of serum biomarkers of AEC and endothelial injury and ECM remodeling in community dwelling adults.

Specific Aim 2: Determine whether CPAP use is associated with reductions in AEC and endothelial injury and ECM remodeling biomarkers in adults with moderate-to-severe OSA. Using stored serum samples from the HeartBEAT and BestAIR trials, we will assess serum MMP-7, SP-D, SP-A, and Ang-2 levels in adults with moderate-to-severe OSA after randomly allocated CPAP or no-CPAP. We hypothesized that CPAP use will be associated with reductions in these biomarkers. This hypothesis has been proven incorrect. Contrary to our hypothesis, the levels of four biomarkers of lung inflammation and extracellular remodeling were not reduced by CPAP in patients with OSA. Indeed, CPAP therapy was associated with an increased circulating level of Ang-2, an endothelial growth factor that is released from pulmonary endothelial cells in the setting of acute lung injury. This finding raises the possibility that CPAP, by increasing alveolar distension, may exacerbate processes that contribute to lung inflammation in OSA.

Original Specific Aim 3: 1) Determine whether untreated OSA promotes AEC and endothelial injury and ECM remodeling biomarkers in adults with ILD and OSA compared with those without OSA; 2) Determine prospectively whether clinically-initiated 4-week PAP therapy increases markers of alveolar endothelial lung injury in OSA.

The results of **Aim 2** analysis indicating potential harm associated with CPAP therapy in OSA necessitated revision of the original aim 3. The **revised Aim 3** is: a) to determine prospectively whether clinically-initiated 4-week PAP therapy increases markers of alveolar endothelial lung injury in OSA; b) to determine whether untreated OSA promotes AEC and endothelial injury and ECM remodeling biomarkers in adults with ILD and OSA compared with those without OSA. Rationale behind revision of Aim 3: Considering that CPAP unexpectedly increased a marker of alveolar endothelial injury in OSA patients without known ILD, we think it is essential to

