Sampling frames and participants: Participants will be sampled from two completed clinical trials: the HeartBEAT and BestAIR trials. Each trial shares common design features and study eligibility criteria with a few exceptions, notably the timing of the measurement of the primary endpoint. Both were designed to test the hypothesis that active CPAP compared to a control intervention improves 24-hour blood pressure in patients with moderate-to-severe OSA and cardiovascular risk factors. The results of the HeartBEAT trial have been reported in the New England Journal of Medicine²³. It was a four-site, three-arm, parallel group, randomized trial of 12 weeks of CPAP, oxygen supplementation, or healthy lifestyle and sleep education for adults aged 45 to 75 years with moderate-to-severe OSA (AHI > 15/hr) and either²³ coronary artery disease or²⁴ three or more cardiovascular risk factors²³. Those with heart failure, a resting SpO₂ < 90%, any current use of supplemental oxygen, or current smoking were excluded. All HeartBEAT participants with available serum who were randomized to the CPAP arm or the healthy lifestyle and sleep education arm (n = 200) will be included in this Aim (those randomized to oxygen will not be included in this Aim). The BestAIR trial is a two-site,

randomized trial comparing active CPAP (with or without behavioral support for CPAP use) to control interventions (education with or without sham CPAP) over 6 to 12 months of follow-up²⁴. For the purpose of this analysis, all individuals receiving active CPAP will be compared to all individuals in the control arms. Inclusion criteria were similar to the HeartBEAT trial: age 45 to 75 years with moderate-to-severe OSA (AHI > 15/hr) with clinical heart disease, diabetes or >3 cardiovascular risk factors. All BestAIR participants will be included (n = 169).

Exposure measurement: We will use the original randomized allocation assigned in the two trials as our primary exposure. In both trials, participants were randomly assigned with equal probability to treatment arms using a stratified permuted block design with stratification by recruitment site and presence of coronary artery disease.

Outcomes: We will measure MMP-7, SP-D, SP-A, and Ang-2 in baseline and follow-up (3 months in HeartBEAT; 6 months in BestAIR) morning fasting sera using commercially available ELISA kits as described in Aim 1. These samples are already stored at the University of Vermont.

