This Aim 2 has been completed. We focused on BestAIR and HeartBEAT trials participants with moderate to severe OSA (AHI 15) who adhered with CPAP for 4 h daily. As this adherence level is averaged over all days, it is higher than the conventional clinical target of 4 hours/night for at least 5 nights/week, and was chosen because we expected the effect to be most pronounced in these patients. In addition, this planned “per protocol” analysis, restricting to individuals randomized to CPAP who used it for at least 4 hours/night based on objective monitoring, corresponds with our current Aim 3 study design. However, contrary to our hypothesis, the levels of four biomarkers of lung inflammation and extracellular remodeling were not reduced by effective PAP therapy in OSA patients. In fact, effective PAP therapy was associated with an increased circulating level of Ang-2, an endothelial growth factor considered a marker of acute lung injury.

Given the limited biospecimen resource, we re-evaluated the markers planned for analysis and decided to substitute osteopontin for SP-A, as a putative marker of fibrogenesis and ECM remodeling, and therefore likely to provide more valuable information than SP-A. SP-A had been identified as a marker of AEC injury; however, it was felt that SP-D is a better marker of the same domain, and the redundancy was not needed, especially considering limited biospecimen resources.

Revised Specific Aim 3: a) to determine prospectively whether clinically-initiated 4-week PAP therapy increases markers of alveolar endothelial lung injury in OSA. b) to determine whether untreated OSA promotes AEC and endothelial injury and ECM remodeling biomarkers in adults with ILD and OSA compared with those without OSA.

Study Design & Sampling Frame: We will perform a prospective study. We will sample participants from the New York Presbyterian/Columbia Pulmonary Fibrosis Foundation Care Center and from The Columbia University Center for Sleep Medicine.

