Phlebotomy will be performed via venipuncture. Morning fasting blood with tourniquet time < 2 min. will be drawn. Samples will be processed within 30 minutes and stored at -80°C. Mid-stream urine will be collected.

Six-minute Walk Test (6MWT), Spirometry, and DLCO will be performed by trained staff in accordance with ATS/ERS guidelines.

Participants will complete Epworth Sleepiness Scale (ESS). These questionnaires will be administered according to the instructions provided in the attached documents.

RECRUITMENT AND CONSENT

Patients with ILD will be recruited from the ILD center. Patients who express interest in the study will be referred to the study team, and study team members will approach interested patients to provide additional information about the study. HIPAA form D is required for study investigators and research team to pre-screen and identify patients from the clinical practice who have met the inclusion criteria. These participants will be approached during their regularly scheduled clinic visits and given information about the study. For “OSA only” cohort, they will be recruited from the Center for Sleep Medicine after their OSA diagnosis had been confirmed clinically by polysomnography. All patients in the Center for Sleep Medicine will be screened for eligibility, and those that are eligible based on inclusion and exclusion criteria will be approached by phone call. Enrollment and consent will occur during the research visit.

RESEARCH AIMS & ABSTRACTS

Research Questions/Hypotheses:

Specific Aim 1: Determine whether greater OSA severity is associated with higher levels of serum biomarkers of AEC and endothelial injury and ECM remodeling in community dwelling adults. We hypothesize that a higher obstructive AHI is associated with greater serum MMP-7, SP-D, SP-A, and Ang-2 levels in 1,830 MESA Sleep Study participants after controlling for potential confounders.

Specific Aim 2: Determine whether CPAP use is associated with reductions in AEC and endothelial injury and ECM remodeling biomarkers in adults with moderate-to-severe OSA. Using stored serum samples from the HeartBEAT and BestAIR trials, we will perform randomized comparisons of serum MMP-7, SP-D, osteopontin, and Ang-2 levels in 369 adults with moderate-to-severe OSA who received CPAP or control interventions. We hypothesize that CPAP use will be associated with reductions in these biomarkers.

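### Aim 2 names randomized allocation as its primary exposure, but its only result with a stated population is in CPAP adherers; the Aim 3 revision and the 78-patient power statement do not say which result they rest on.

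*Combined protocol and SAP*

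**What the plan says.** **Planned Aim 2 analysis.** Under Study Design, Aim 2, Exposure measurement: "We will use the original randomized allocation assigned in the two trials as our primary exposure". The sampling text takes 200 HeartBEAT participants (CPAP and education arms) and all 169 BestAIR participants. Research Questions/Hypotheses repeats the intention: "we will perform randomized comparisons of serum MMP-7, SP-D, osteopontin, and Ang-2 levels in 369 adults".

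**Reported Aim 2 analysis.** The completion note that closes the Aim 2 section describes a per-protocol analysis "restricting to individuals randomized to CPAP who used it for at least 4 hours/night based on objective monitoring". It calls this analysis planned, says the adherence level "was chosen because we expected the effect to be most pronounced in these patients", and says the analysis "corresponds with our current Aim 3 study design". It reports no fall in the four biomarkers and a higher Ang-2 with effective PAP.

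**Use of the result.** Study Purpose and Rationale says of the Aim 2 hypothesis: "This hypothesis has been proven incorrect". It gives the Ang-2 finding for CPAP without mentioning use. It then cites the Aim 2 "analysis indicating potential harm associated with CPAP therapy in OSA necessitated revision of the original aim 3", on the ground that "CPAP unexpectedly increased a marker of alveolar endothelial injury in OSA patients without known ILD".

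**Aim 3a.** The same section sizes the before-and-after cohort at 78 for 80% power at two-sided 0.05, using effect size and SD estimates from the two trials. Neither number is printed, and the analysis set that supplied them is not named. Selection Criteria sets no adherence requirement. Study Procedures says that CPAP is prescribed clinically in this cohort and is not a study procedure.

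**The concern.** Adherence is observed after randomization and is related to patient characteristics. Whether adherers are compared with controls or with their own baseline, the comparison loses the protection of randomization. That is acceptable in a labelled secondary analysis. It is not a substitute for the exposure that the plan declares primary, and no result for that exposure is identified anywhere.

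Two things are at stake:

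- **The basis for the Aim 3 revision.** The opening rationale describes randomly allocated CPAP and then gives the finding for CPAP in general. A reader would naturally take the signal behind the revision to be a randomized one.
- **The match between Aim 3a and its source.** The 78 patients are meant to validate the Aim 2 signal. If that signal came from adherers, a cohort analysed regardless of use targets a different and probably smaller mean effect. Without recorded hours of use, the adherer population could not be reconstructed.

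**Working it through.** **Step 1. Set the sections side by side.**

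| Place | Population or exposure |
|---|---|
| Aim 2, Sampling frames and Exposure measurement | By allocation; 200 + 169 = 369 |
| Research Questions/Hypotheses, Aim 2 | Randomized comparison, 369 adults |
| Aim 2 completion note | CPAP-arm participants with at least 4 h/night; no n, comparator, estimate or CI |
| Study Purpose and Rationale, Aim 2 | CPAP, with no condition on use |
| Sample-size statement for the 78 | Effect seen in Aim 2; analysis set not named |
| Selection Criteria, OSA patients | No adherence criterion |
| Data listed under Statistical Procedures and Study Procedures | Hours of PAP use not listed |

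The planned total of 369 agrees across sections. The adherence analysis appears only in the completion note. The Aim 2 design text and the Research Questions section do not describe it.

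**Step 2. Back-solve the 78.** No effect size or SD is printed, so the figure cannot be reproduced forward. The test is not named either; I assume a paired comparison of before and after.

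- Normal approximation: d = (1.960 + 0.842)/√78 = 0.317 SD of the change.
- Noncentral t: 80% power at d = 0.321.

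This is the effect implied by 78 and 80%. It cannot be checked against Aim 2.

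**Step 3. Illustrate the dilution.** Suppose d is the adherer effect, and the mean effect in all 78 is f × d with the SD of the change held constant. Then

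power ≈ Φ(f × 2.802 − 1.960).

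The unprinted effect size cancels, so the result depends only on f.

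| f | Power with 78 |
|---|---|
| 1.0 | 80% |
| 0.8 | Φ(0.281) = 61% |
| 0.7 | Φ(0.001) = 50% |
| 0.6 | Φ(−0.279) = 39% |
| 0.4 | Φ(−0.839) = 20% |

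The noncentral t gives the same percentages after rounding.

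If a share a of patients adhere and non-adherers get a fraction h of the effect, then f = a + (1 − a)h. The documents give neither a nor h. Assuming a = 0.4 to 0.6:

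- h = 0.5: f = 0.4 + 0.6 × 0.5 = 0.7 up to f = 0.6 + 0.4 × 0.5 = 0.8, so power is 50–61%.
- h = 0: f = 0.4 to 0.6, so power is 20–39%.

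**Step 4. The alternative analysis set.** Under the same assumed shares, an adherers-only analysis would have 0.4 × 78 ≈ 31 to 0.6 × 78 ≈ 47 pairs. At d = 0.321 the noncentral t gives 41% and 58%.

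**Step 5. The other branch.** If the effect behind the 78 is the allocation effect, it already averages over mixed use in the source trials, and the dilution in Step 3 does not arise in this form.

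**The case against.** The strongest reply has four parts.

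**The opening rationale may be reporting an allocation-based result.** It follows directly on a description of random allocation, and the completion note says that the work focused on adherers, not that only adherers were analysed. This stands as a possibility. A reader might infer that the Aim 3 revision certainly rests on a non-randomized signal, or that the allocation analysis was never done. The documents do not establish either. Near-identical wording makes a single analysis likely, not certain.

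**The restriction is disclosed and called planned.** This is true, so the analysis should not be described as unplanned or concealed. The Aim 2 title also asks about CPAP use, which fits an analysis by use. Even so, the plan makes allocation primary, and the sections that describe the Aim 2 analysis contain no adherence analysis.

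**A status note is not a results section, and the claims are modest.** Missing detail in a short note is not in itself a defect of the Aim 3 plan. Some wording is hedged, and the signal is presented as something to validate prospectively. But the result is also the stated reason for the revision and the source of the sample size, so its provenance still matters. The two unhedged statements quoted above remain.

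**The power figures rest on assumptions.** They do. The documents supply only 78, 80% and 0.05. The list of clinical data is also not worded as exhaustive, so usage might be captured without being named.

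**Conclusion.** The point holds as a problem of provenance and mismatch. The declared primary Aim 2 comparison has no identified result. The one result with a stated population is a post-randomization selection, and the text that revises Aim 3 does not say which analysis it rests on. The adherer analysis is said to match an Aim 3 design that has no adherence criterion and no listed usage data.

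The effect on power is conditional. If the 78 were sized on the adherer effect, 80% does not apply to all 78 with mixed use. It would be 50–61% at a mean effect of 70–80% of the adherer effect, and lower with more dilution. These figures assume a paired test, a constant SD of change and dilution fractions that are not in the documents. If the 78 were sized on the allocation effect, there is no shortfall of this kind.

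A reader might conclude that Aim 3a is underpowered at 20–39%, or that enrolment must rise. The documents do not support this: the low range needs an adherer source for the effect, 40–60% adherence and no effect at all in non-adherers, and none of these is stated. The sponsor should act on the point; confidence is medium because the source of the effect is not stated.

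**What to change.** 1. **Aim 2 section.** Report the comparison by randomized allocation as the primary result, with its CI, or reference it if already done. Label the adherer result secondary and non-randomized, and give its comparator and n.
2. **Study Purpose and Rationale.** Carry that label forward. Replace "This hypothesis has been proven incorrect" and "CPAP unexpectedly increased a marker of alveolar endothelial injury in OSA patients without known ILD" with wording that names the population analysed and gives the estimate.
3. **Aim 3a.** State the effect size, SD and source population behind the 78. Say whether the analysis covers all 78 or adherers only. List device-recorded PAP hours as collected data, so that an adherer analysis is possible. If the source and analysis populations differ, restate the power for 78; more enrolment is not required.

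The cost is wording changes, a restated power calculation, retrieval of usage records and, if not already done, a re-analysis of data in hand. The downside is that the Ang-2 estimate or the stated power may become less favourable.

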Assessment of Continuous Positive Airway Pressure Therapy in OSA and ILD

ClinicalTrials.gov ID: **NCT03901534**

Date of IRB approval: **June 3, 2024**

BACKGROUND

Study Purpose and Rationale

Idiopathic pulmonary fibrosis (IPF) is a progressive fibrotic disease of the peripheral lung parenchyma that affects 0.5% of older adults in the U.S. and confers a median survival of only 3.8 years.¹⁻³ While pirfenidone and nintedanib slow disease progression, neither drug reverses fibrosis nor prevents ongoing subclinical alveolar epithelial cell (AEC) injury, the antecedent cause of fibrosis in IPF.^{4,5} We and others have shown that subclinical AEC injury as well as extracellular matrix (ECM) remodeling are also detectable using serum biomarkers, including increases in surfactant protein-D (SP-D), Krebs von den Lungen-6 (KL-6), and MMP-7 (a marker of AEC injury and ECM remodeling). Each of these biomarkers is also elevated in IPF and other fibrotic ILDs.⁶⁻¹¹ We and others have found that obstructive sleep apnea (OSA), a condition that is highly prevalent in adults with fibrotic interstitial lung diseases, including IPF, is also associated with increases in serum KL-6, SP-A and MMP-7, and with angiopoietin-2 (Ang-2; an endothelial marker), and that OSA is associated with subclinical ILD on CT.¹²⁻¹⁵ These data support (1) the use of serum biomarkers to detect subclinical AEC injury and ECM remodeling, and (2) the hypothesis that OSA may contribute to subclinical AEC injury. Based on these data, our central hypothesis is that moderate-to-severe obstructive sleep apnea causes subclinical AEC injury and, in susceptible individuals, peripheral lung fibrosis and fibrotic ILD.¹⁶ OSA might lead to AEC injury and ECM remodeling by exerting peripheral stretch of the lung, which has been hypothesized to be an underlying cause of IPF and other fibrotic ILDs.^{12,13} Obstructive apneas and hypopneas are characterized by repetitive forceful inspiratory efforts against a completely or partially closed airway.¹⁷ This causes wide swings in pleural pressure exerting peripheral tractional stress on the lung, potentially causing stretch and injury to AECs analogous to that which occurs during positive pressure ventilation.¹⁸⁻²⁰ Other mechanisms linking OSA and subclinical AEC injury are possible, including promotion of oxidative injury by intermittent hypoxia and microaspiration from gastroesophageal reflux disease (GERD).^{21,22} We propose to leverage the Multi-Ethnic Study of Atherosclerosis (MESA) Sleep Study, a community-based cross-sectional study, the HeartBEAT and BestAIR randomized clinical trials of CPAP for OSA, and an inception cohort of ILD patients diagnosed with OSA. We propose to establish OSA as a modifiable contributor to AEC and endothelial injury and thereby provide

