validate these findings in a prospective cohort and to document prospectively whether untreated OSA worsens existing lung injury in patients with concomitant ILD. We will use a two-pronged approach to address this question: 1) We plan to recruit prospectively additional 78 patients with untreated moderate-to-severe OSA and assess the above biomarkers of alveolar endothelial injury before and after 4 weeks of clinically-initiated PAP therapy (not randomly allocated owing to the well-recognized societal hazard posed by untreated OSA patients with daytime somnolence). Using the effect size and SD estimates from the HeartBEAT and BestAir samples, a sample of 78 patients will provide 80% power to detect an effect of the size that we observed in **Aim 2** with $\alpha(2) = 0.05$; 2) We will recruit all participants as planned for **Aim 3** (anticipated 100 patients with ILD and concomitant OSA and 65 patients with ILD who do not have OSA) and compare their baseline levels of alveolar epithelial and endothelial injury biomarkers. This approach is crucial to establish whether patients with concomitant ILD and OSA have a greater degree of alveolar endothelial injury compared with ILD patients without OSA. If OSA turns out not to contribute independently to alveolar endothelial injury, this information would also be valuable considering that PAP may worsen existing alveolar endothelial injury in ILD patients, which suggest that alternative treatments for OSA that do not increase alveolar distension (for example, oral appliances) may be particularly suitable for patients with concomitant ILD and OSA. After validating our findings from Aim 2 as described above, we will explore in future studies whether oral appliances lower markers of AEC and endothelial injury in ILD patients with OSA.

Study Design

Aim 1: Determine whether the greater OSA severity is associated with higher levels of serum biomarkers of AEC and endothelial injury and ECM remodeling in community dwelling adults. We will perform cross-sectional analyses in this Aim.

Sampling frame and participants: We will sample participants from the MESA Sleep Study. We will sample the 1,830 MESA Sleep study participants who have available polysomnography data and no self-reported lung disease. We realize that a small proportion of participants will have missing or low-quality samples.

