Measurement of exposures: The primary exposure of interest will be the obstructive AHI, defined as the number of all obstructive apneas and hypopneas with >4% desaturation during sleep divided by the # of hours of sleep. We will also examine the number of obstructive apneas and hypopneas regardless of desaturation observed per hour of sleep, the proportion of sleep time with obstructive apneas and hypopneas, nadir and average oxyhemoglobin saturation (SpO₂), the percentage of sleep time with an SpO₂ 3% desaturation or arousal. We also will explore indices specific to sleep state (REM/NREM), and oxygen desaturation events occurring without prior apneas/hypopneas.

Measurement of outcomes: Our outcomes of interest are 4 serum protein biomarkers. Laboratory analyses using MESA Exam 5 morning fasting serum will be performed using quantitative sandwich ELISA assays from R&D Systems (MMP-7, SP-D, Ang-2) and Biovendor (SP-A) at the MESA Core Laboratory at the University of Vermont where these samples are stored.

Aim 2: Determine whether CPAP use is associated with reductions in AEC and endothelial injury and ECM remodeling biomarkers in adults with moderate-to-severe OSA.

Study Design: Retrospective cohort study using data and biosamples from two previously performed studies.

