Selection Criteria, Expected Enrollment, and Screening: This study plans to enroll approximately 165 subjects with interstitial lung disease. We anticipate that 100 of those will have concomitant OSA and 65 will not have concomitant OSA. We will enroll 78 OSA patients from The Columbia University Center for Sleep Medicine and assess the above biomarkers of alveolar endothelial injury before and after 4 weeks of clinically-initiated PAP therapy (not randomly allocated owing to the well-recognized societal hazard posed by untreated OSA patients with daytime somnolence).

Inclusion Criteria for Patients with ILD:

1. Informed consent
2. Age 18 years or greater
3. Diagnosis of any of the following fibrotic interstitial lung diseases as defined by ATS/ERS/JRS/ALAT guidelines and research statements and Delphi surveys^{3, 4, 5}:
Idiopathic pulmonary fibrosis - Idiopathic non-specific interstitial pneumonia (NSIP) with fibrosis - Chronic hypersensitivity pneumonitis with fibrosis - Connective tissue disease related interstitial lung disease (CTD-ILD) - Unclassifiable idiopathic interstitial pneumonia with fibrosis

Exclusion criteria for Patients with ILD:

1. Clinically significant lung disease other than fibrotic interstitial lung disease
2. Planned change to the IPF treatment during the study period
3. Current cigarette smoking (past 4 weeks)

4. Lower respiratory tract infection in past 60 days. (Upper respiratory tract infection is not a contraindication)
5. History of life threatening cardiac arrhythmias
6. Known chronic heart failure (LVEF < 45% or echo evidence of RV dysfunction or PH)
7. Chronic opiate analgesic use
8. History of sleepiness-related automobile accident within past year of enrollment
9. Expected survival time in the opinion of the investigator of less than 6 months
10. History of stroke or spinal cord injury

Study Overview: After informed consent and review of inclusion/exclusion criteria, study participants will undergo full-night polysomnography at their baseline visit (see below).

Phlebotomy, spirometry, 6-minute walk test, diffusing capacity, and questionnaires completed at the research visit.

Inclusion criteria for OSA patients:

1. Age >18 years
2. Clinical diagnosis of untreated OSA documented by nocturnal polysomnography.

Exclusion criteria for OSA patients:

1. Current treatment with CPAP or oral appliance
2. Identical exclusion criteria as for ILD patients

STATISTICAL PROCEDURES

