Outcome measures: 1) Determine whether untreated OSA promotes AEC and endothelial injury and ECM remodeling biomarkers serum (MMP-7, SP-D, osteopontin and Ang-2) in adults with ILD and OSA compared with those without OSA; 2) Determine prospectively whether clinically-initiated 4-week PAP therapy increases markers of alveolar endothelial lung injury (MMP-7, SP-D, osteopontin and Ang-2) in OSA. All assays will be performed in [name] lab as described in Aim 1. Secondary outcomes will include changes in FVC, DLCO, 6-minute walk distance, dyspnea, and HRQOL.

Data Management: We will use a REDCap database for data entry and management as we have previously done in the Lung Transplant Body Composition Study.

STUDY PROCEDURES

For patients with ILD, after informed consent and review of inclusion/exclusion criteria, study participants will undergo home polysomnography (see below). Phlebotomy, spirometry, diffusing capacity and questionnaires will be measured at the research visit.

Participants with ILD will undergo home polysomnography (PSG) after they have consented to the study. We will use the Nox A1 sleep recorder manufactured by Nox Medical (Reykavik, Iceland) for the home PSG recordings. This will strictly be a research study and not meant for clinical purposes. PSG devices will be returned to Columbia and recordings uploaded by the research team. After being uploaded, studies will be exported in standardized format (European Data file; edf) and transferred by secure FTP to the Sleep Reading Center at Brigham & Women's Hospital for scoring by a single research sleep technologist according to well-established protocols. Brigham Sleep Reading Center will perform interpretation using standard AASM scoring criteria.

For patients with OSA only (without ILD), they will undergo clinically indicated polysomnography in the Center for Sleep Medicine. The investigators have no role in determining the need for polysomnography or CPAP therapy in this OSA only cohort. CPAP will be prescribed by their clinician provider and not by the study investigators. Therefore, polysomnography and CPAP are not considered study procedures for OSA only cohort.

Supplemental oxygen: If participants use supplemental oxygen while sleeping at baseline, they will use their supplemental oxygen as prescribed by their healthcare provider during the home PSG.

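### Aim 3b compares ILD patients with and without OSA with no AHI cut-off and no continuous-AHI analysis, so the result depends on a split that could be chosen after the data are seen

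*Combined protocol and SAP*

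**What the plan says.** **Aim 3b.** Under Selection Criteria, Expected Enrollment, and Screening: "This study plans to enroll approximately 165 subjects with interstitial lung disease", and "We anticipate that 100 of those will have concomitant OSA and 65 will not have concomitant OSA". The Background (rationale for the revised Aim 3) says that the investigators will "compare their baseline levels of alveolar epithelial and endothelial injury biomarkers". Outcome measures frames the objective as markers "in adults with ILD and OSA compared with those without OSA". The markers are MMP-7, SP-D, osteopontin and Ang-2.

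**How OSA is established in the ILD cohort.** Each ILD participant has home polysomnography, scored at one reading center. Study Procedures states: "Brigham Sleep Reading Center will perform interpretation using standard AASM scoring criteria". That names rules for scoring recordings. It gives no AHI value above which a patient counts as having OSA.

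**AHI elsewhere.** For Aim 1, Measurement of exposures says: "The primary exposure of interest will be the obstructive AHI". Research Questions/Hypotheses states the Aim 1 hypothesis in graded form (higher AHI, higher marker), with control for confounders. A figure of 15/hr appears only for Aim 2, for instance in its description of one source trial: "adults aged 45 to 75 years with moderate-to-severe OSA (AHI > 15/hr".

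**Analysis model.** The text under Statistical Procedures covers measurements, outcomes and data management. It contains no test, model or covariate list for Aim 3b.

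**The concern.** Two problems meet here.

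First, the groups are undefined. The Background puts the hypothesis in terms of severity ("our central hypothesis is that moderate-to-severe obstructive sleep apnea causes subclinical AEC injury"), but Aim 3b says only OSA. Patients with mild OSA could be placed in either group. If the choice is made once AHI and biomarkers are both available, several versions of the result are possible for each of four markers.

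Second, if the only analysis is a two-group contrast, graded information that is already being collected goes unused in a sample fixed at about 165. The Background says that finding no independent contribution of OSA would also be valuable, because it bears on the choice of OSA treatment in ILD. An avoidable false null therefore has a cost.

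Stating a cut-off would cure the first problem but not the second.

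**Working it through.** There is no planned figure to reproduce. The only power statement (78 patients, 80%, two-sided 0.05) belongs to Aim 3a. Aim 3b has no stated effect size, SD, alpha or power.

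**Inputs from the documents.** N = 165 and split 100/65 (Selection Criteria). OSA prevalence of 59-88% in IPF (Scientific Abstract). AHI 15/hr (Aim 2). All distributions and shapes below are assumptions, because the documents give none.

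**1. Information kept by the split, normal exposure and linear effect.**
- p = 100/165 = 0.606; p(1-p) = 0.2388; |z| = 0.269.
- Efficiency = phi(z)² / [p(1-p)] = 0.3848² / 0.2388 = 0.620. The loss is 38.0%.
- Effective size = 0.620 × 165 = 102.

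**2. The same in power terms (Fisher z, two-sided 0.05).**
- Correlation detectable with 80% power using continuous AHI: tanh[(1.960 + 0.842)/√162] = 0.217.
- After the split it becomes 0.217 × √0.620 = 0.171, with power of about 59%.
- Conversely, a correlation that gives the split 80% power (0.217/√0.620 = 0.275) gives continuous AHI about 95%.

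**3. Other splits, same model.** The loss is 36% at 50:50, 37.5% at 59% with OSA and 62% at 88%. The 59-88% range is for IPF, whereas Aim 3b enrolls five categories of fibrotic ILD and anticipates 61%. The 88% case is an outer bound, not an expectation.

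**4. Other shapes, 100/65 split.** Loss = 1 - corr²(exposure, group).

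| Assumption | Loss from the split |
|---|---|
| Effect linear in AHI, AHI uniform: 1 - 3p(1-p) | 28% |
| Effect linear in AHI, AHI exponential: 1 - (p ln p)²/[p(1-p)] | 61% |
| Effect linear in raw AHI, AHI log-normal, log-SD 0.5 to 1.2 | 56% to 86% |
| True step exactly at the cut-off | 0% |

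In the last row the linear continuous analysis is the one that loses 38% (normal exposure). That advantage depends on the cut-off falling near the step. If the true step separates the top 30% of patients and the split is at 60.6%, the split's efficiency is 0.30 × 0.394/(0.606 × 0.70) = 0.28, against 0.58 for the linear analysis. With the true step at the top 50%, the two are nearly equal (0.65 and 0.64).

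**5. Dependence on the cut-off.** Assume log-normal AHI with log-SD s between 0.8 and 1.2. Setting 100 of 165 at or above cut-off c gives mu = ln c + 0.269s, and the number at or above k is 165 × [1 - Φ((ln k - mu)/s)]. The value 5/hr is an illustrative lower cut-off and is not in the documents.
- If 100 have AHI ≥ 15, then 146 to 157 have AHI ≥ 5.
- If 100 have AHI ≥ 5, then only 22 to 43 have AHI ≥ 15.

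Moving between these two cut-offs reclassifies roughly 46 to 78 patients (146 - 100 = 46; 100 - 22 = 78). This step needs no assumption about how the marker relates to AHI.

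**The case against.** A reader might infer that the plan has chosen a dichotomy over the Aim 1 method and thereby throws away 38% of its information. The documents do not support that. No Aim 3b model is stated, so continuous AHI is unplanned but not ruled out. The 38% is the value for a normal exposure with a linear effect, and neither condition is documented.

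Nor do the documents give Aim 1 a regression of log marker on log AHI. They name the exposure and a graded hypothesis, and the Lay Abstract describes Aim 1 as people with versus without sleep apnea.

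There is also a substantive case for groups. The central hypothesis is worded by severity category, and the Background asks whether patients with both conditions have more injury than those with ILD alone. A slope does not answer quite the same question. This stands as a reason to keep the group contrast, but as a secondary result. It is not a reason to leave the groups undefined, and a step at some AHI is no more documented than linearity.

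Two practical points also stand. A contrast at 15/hr puts all mild OSA in the comparison group, so a single cut-off is not enough. Participants who use oxygen at night will use it during the recording, and Aim 1's AHI has a desaturation criterion (>4%), so AHI may be understated in oxygen users. A cut-off on the same AHI would be affected too.

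**Conclusion.** The point holds in this form: Aim 3b has no stated definition of its exposure groups and no planned use of AHI as a continuous measure, although that measure is being collected. Dependence on an unstated cut-off is the firmer part. It follows from the text, and the reclassification count needs only an assumed AHI distribution.

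The information loss is conditional: about 38% under a normal (log) AHI and a linear relation, and from 0% to 86% across the shapes examined. Quoting 38% as a property of this plan would go too far. This is an inexpensive improvement that should be made. It does not show that the comparison is invalid.

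**What to change.** Before AHI is linked to the biomarkers, write into the plan:

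- **Primary Aim 3b analysis:** regression of log marker on continuous obstructive AHI, using the AHI definition in Aim 1, a stated transform such as log(AHI+1) (my proposal; Aim 1 gives no transform), a prespecified confounder list and a spline check of shape.
- **Secondary:** the two-group contrast at AHI 15/hr, the threshold used for Aim 2, with one other prespecified cut-off as a sensitivity analysis.
- **Oxygen:** a sensitivity analysis that excludes or adjusts for participants who slept on prescribed oxygen, or that uses the index counting events regardless of desaturation, which Aim 1 already lists.

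This needs no new patients, visits or assays. The cost is a shape assumption, which the spline examines, and a little more analysis work.
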